6.5.9 Unscheduled Visits/Lead Replacements

Subjects may require an unscheduled visit if they experience a technical issue with the stimulation system that the clinical staff has difficulty resolving, desire adjustments to stimulation parameters, require a bandage change or lead replacement, or experience an adverse event which requires further evaluation by the clinical study staff. Communication with the subject for minor issues (e.g., technical issues that can be easily resolved) will not be considered as unscheduled visits, but will be recorded in the Communications Log.

This decision will be at the discretion of the Subject, Investigator and the Sponsor and should take into account the following considerations

- 1) the subject's desire to continue with the therapy and understanding that the same risks of the initial lead placement would apply again,
- 2) the Investigator's belief that the intended target location is healthy enough to place another lead and there are no concerns with patient compliance with the care of the lead exit site, and
- 3) the amount of time remaining in the home trial.

Alternatively, if one lead fails to improve postoperative pain, then the subject may continue using only the effective lead (i.e., one system).

Any additional lead placements will involve additional instances of Visit 2 (described above) and the associated requirements (e.g., subjects who initially required an INR test prior to the first lead placement will have the test repeated as necessary). Subjects will then receive the remaining balance of the stimulation therapy. Subjects will have an additional exposure to the risks of lead placement, but the risks are the same as the risks detailed for the initial procedure (Section 12).

6.6 Study Visit Windows

The acceptable windows for each visit are listed below in **Table 1**.

Table 1 Study Visit Windows

Visit Number	Visit Name	Window
1	Baseline	
2	Lead Placement and Testing	
3	Follow-up phone call	
4	Day of TKA (POD 0; start of stimulation)	
5a, b, c...	Daily in-hospital visits	
6	1 week treatment phone call	
7	2 weeks treatment in-person visit	
8	3 weeks treatment phone call	
9	4 weeks treatment phone call	
10	5 weeks treatment phone call	
11	6 weeks treatment in-person visit (End of Treatment)	
12	2 months post TKA phone call	
13	3 months post TKA in-person visit	

6.7 Study Duration

The duration of this study is expected to be approximately 2 years. We anticipate enrolling 2 subjects per month. Each subject's participation will last approximately 4 months.

6.8 Early Termination

It is possible that this study may be terminated prior to enrolling 36 subjects. As a result of the study design, the results will be reviewed and evaluated throughout the study as each subject completes his/her participation. If the results are less favorable than anticipated the study may be terminated early. Similarly, if it is found that the study yields results that are more favorable than expected, the study may be terminated earlier than expected. Any decision to terminate the study will be promptly reported to the IRBs and FDA.

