Exclusion Criteria	
 • Body Mass Index (BMI) > 40 kg/m² • Compromised immune system based on medical history • History of valvular heart disease • Implanted cardiac pacemaker/defibrillator or Deep Brain Stimulator • Evidence of joint or overlying skin infection of the affected limb • History of recurrent skin infections • Bleeding disorder OR INR ≥ 1.5 for those on warfarin • Confounding conditions • History of nerve damage in the affected lower limb • Allergy to skin surface electrodes and/or medical-grade adhesive tapes • Allergy to all local anesthetic agents such as lidocaine or previous reaction to anesthesia • Any other medical condition that may interfere with ability to participate in a clinical trial as determined by the Investigator • Prisoners, minors, legally incompetent people, unconscious patients, house staff, or students • Pregnant • History of substance abuse within 6 months • Potential secondary gain issues
Primary Safety Endpoint	Occurrence of device-related adverse events.
Primary Clinical Endpoint	Subjects will record average pain while walking over the last 24 hours in a daily diary using the 11-point numerical rating scale (0=no pain to 10=worst pain imaginable) of the Brief Pain Inventory – Short Form (Question 5; BPI-5). The mean of the daily scores recorded will be calculated, and the primary endpoint is the mean pain score across all subjects. The primary endpoint will be compared to historical controls (e.g., published data).
Secondary Endpoints	
Pain-related outcomes
 
 • Pain intensity over the last 24 hours as recorded as Average pain on a numerical rating scale (BPI-5) using a daily diary • Pain intensity over the last 24 hours as recorded as Average pain at rest on a numerical rating scale (BPI-5) using a daily diary • Cumulative analgesic usage

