Existing treatments for postoperative pain include analgesics, continuous passive motion, cooling pads, epidural analgesia, and regional nerve blocks (anesthetic delivered continuously through a percutaneously placed catheter or as single injections). In spite of these treatments, most patients experience moderate to severe acute pain. Further, during the subacute phase, these treatments are ineffective, are not indicated for such an extended period of time or for at home use, and/or carry risks of side effects and complications. As a result, a non-opioid treatment is needed that can relieve postoperative pain following TKA with minimal side effects and can be used throughout the duration of the subacute phase. The proposed study will determine the feasibility of using PNS therapy to treat postoperative pain following TKA. The hypothesis is that percutaneous stimulation will evoke a [REDACTED] sensation [REDACTED] in the region of pain and produce clinically significant reductions in pain.

Subjects will receive leads to stimulate the nerves innervating the regions of pain or expected pain [REDACTED] up to 2 weeks prior to TKA surgery. Stimulation may be delivered up to the time of the TKA. Following TKA, stimulation will be turned on and adjusted as needed to provide pain relief. Subjects will record average pain over the last 24 hours in a daily diary using the 11-point numerical rating scale (0=no pain to 10=worst pain imaginable) of the Brief Pain Inventory – Short Form (Question 5; BPI-5). The mean of the daily scores recorded from POD0 to POD28 (i.e., first 4 weeks following TKA surgery) will be calculated, and the primary endpoint is the mean pain score across all subjects, which will be compared to historical controls (e.g., published data). Subjects will receive treatment for up to 24 hours/day for up to 60 days (i.e., leads will be indwelling for up to 60 days total). Subjects will be followed for three months following TKA surgery. The results of this study will [REDACTED] will be used to support subsequent studies of the SPR PNS therapy to treat postoperative pain following TKA.

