The proposed method has been tested to treat pain in patients following TKA in a separate preliminary study.

Three subjects with pain following TKA (range: postoperative day 6-9) were tested with the proposed approach in a non-significant risk case series study.

Summary

Postoperative pain is a substantial problem for a majority of patients following total knee arthroplasty. Present treatments for postoperative pain during the subacute phase (4 – 30 days following surgery) are ineffective, carry risks of side effects/complications, and/or are not indicated for extended use. The proposed therapy using percutaneous electrical stimulation

is expected to reduce postoperative pain and address the shortcomings of existing therapies. The proposed study will determine if this therapy can produce clinically significant reductions in postoperative pain following TKA as compared to historical controls (e.g., published data).

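### Section 6.8 allows a stop for better-than-expected results without any rule; averaged over studies stopped that way, the plain mean in 8.1 overstates benefit

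*Combined protocol and SAP*

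**What the plan says.** Section 5.2 sets a ceiling of 36 subjects. Section 6.8 then states that "the results will be reviewed and evaluated throughout the study as each subject completes his/her participation". It allows a stop in either direction: "If the results are less favorable than anticipated the study may be terminated early", and likewise "if it is found that the study yields results that are more favorable than expected, the study may be terminated earlier than expected". It names no endpoint, threshold, minimum number of subjects or decision maker. No redaction mark appears in that section.

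The plan does expect a benefit. Section 2.1 hypothesises that stimulation will "produce clinically significant reductions in pain", and the summary in 2.2 says the therapy "is expected to reduce postoperative pain and address the shortcomings of existing therapies". No visible text says how large. Parts of 2.2 are blacked out, so a figure may stand there, but 6.8 does not point to one.

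In the Protocol Synopsis, "the primary endpoint is the mean pain score across all subjects". Section 8.1 calculates that mean without an interval or any method for early stopping, and compares it with historical controls, for which published data are given only as an example. Section 7.5 gives data entry and analysis to the sponsor. Section 13.2 adds a general right of the sponsor to terminate, including for valid scientific reasons.

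**The concern.** When enrolment ends because the running results look good, the data in hand at that moment are on average better than the truth, and a plain mean carries that excess into the report. Because the expected result is not defined in visible text, the excess can be neither calculated beforehand nor corrected afterwards.

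Sections 1.5 and 8.0 give the purpose as determining the treatment effect and supporting and refining later studies. Planners of those studies will use the estimate from the study that was run. If it stopped because results looked good, their starting figure is on average too favourable and rests on fewer subjects.

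**Working it through.** **Inputs from the documents.** Cap 36 (5.2). Accrual: "We anticipate enrolling 2 subjects per month" (6.7). Each subject's "participation will last approximately 4 months" (6.7). A review as each subject completes (6.8).

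**Check of the plan's own figure.** Enrolment takes 36/2 = 18 months. Adding 4 months of follow-up gives 22 months, in line with the stated duration of about 2 years. The cap of 36 has no stated derivation, so there is no sample-size figure to reproduce.

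**Subjects in progress.** 2 a month × 4 months = about 8 at any review. A stop after n completers gives n + 8 subjects, so it shortens the study only if n + 8 < 36, that is, n ≤ 27.

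**Formula.** The in-progress subjects played no part in the decision, so their mean is unbiased. For a stop at n:

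bias = n/(n + 8) × E[mean of the n completers − truth | stop at n].

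Counting the 8 dilutes the excess but does not remove it. For example, a one-sided 2.5% t-test at n = 12 needs a mean better than expected by 2.201/√12 = 0.635 sample SDs. After dilution this is 12/20 × 0.635 = 0.38.

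**Simulation.** The documents give no rule, SD or expected size, so these are assumptions: normal outcomes, unit SD, 200,000 studies per cell, first review at n = 5, 8 or 12, reviews up to n = 27, 8 in progress counted, favourable stop only. Rule A stops when the running mean is better than expected by any amount. Rule B stops on a nominal one-sided 2.5% t-test against the expected value at each review. Ranges run over the three first-review times; bias is in SD.

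| Rule | Truth relative to expected | Studies stopped | Overstatement if stopped | Average over all studies |
|---|---|---|---|---|
| A | 0.25 SD better | 96–98% | about 0.03 | 0.02–0.03 |
| A | equal | 73–81% | 0.10 | 0.03–0.05 |
| A | 0.25 SD worse | 31–48% | 0.19–0.23 | 0.03–0.05 |
| B | 0.5 SD better | 80–81% | 0.09–0.10 | 0.03–0.05 |
| B | 0.25 SD better | 37–41% | 0.20–0.21 | 0.03–0.04 |
| B | equal | 7–11% | 0.33–0.34 | 0.01–0.02 |
| B | 0.25 SD worse | 0.7–2% | 0.42–0.49 | 0.00–0.01 |

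Within each rule, the likelier the stop, the smaller the overstatement.

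**Sensitivity.** For rule B with truth equal to expected, 4 in-progress subjects give 0.40–0.42 and 12 give 0.27–0.29. With a z ≥ 1.96 trigger from n = 10, the figure is 0.36 with 8 counted and 0.56 with completers only. For an assumed SD of 1.5 to 2.5 points on the 0–10 scale, 0.10–0.34 SD is 0.10 × 1.5 = 0.15 to 0.34 × 2.5 = 0.85 points, while 0.03 SD is only about 0.05 to 0.08 points.

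**Both stops, as 6.8 is written (rule B).** The average bias over all studies is 0 when truth equals expected and about 0.03 SD in size when it differs by 0.25 SD. The overstatement given a favourable stop does not change.

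**Unfavourable stop only (rule B).** Studies that reach 36 are a selected group, biased toward benefit by about 0.02, 0.08 or 0.18 SD when truth is 0, 0.25 or 0.5 SD below expected.

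**Historical comparator (separate from stopping).** With equal SDs, including the standard error of a source of m patients multiplies the interval width at n = 36 by √(1 + 36/m): 1.41, 1.17 and 1.09 for m = 36, 100 and 200.

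**The case against.** This is a feasibility case series of up to 36 subjects that yields preliminary data. It states no test and no error rate, and it declares its flexibility openly. Section 6.8 requires any termination decision to be reported to the IRBs and FDA. Section 8.0 says all primary and secondary outcome data will be analysed and reported, and the wording of the primary endpoint implies that in-progress subjects are counted. The average bias over all studies is small, and every size above rests on an assumed rule.

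Most of this stands. A reader might infer that a type I error rate is inflated; none is stated, so none is breached. A reader might also infer that any study stopped for good results is overstated by some definite amount. The excess is an average over such studies, its size is unknown, and where a favourable stop is most likely it can be close to nothing. The provisions in 6.8 and 8.0 partly cover disclosure of a stop.

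They do not answer the point itself. Telling oversight bodies of a stop does not change the estimate, and counting in-progress subjects only dilutes the excess. Later planners will use the one study that was run, not the average over all possible studies.

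There is also a fair objection to removing the unfavourable stop: more subjects would have leads placed after results look poor. That is a real trade-off, so the unfavourable stop may stay if it has a rule.

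**Conclusion.** The point holds, as a matter of estimation. Section 6.8 permits a stop for good results without a rule, 8.1 reports an unadjusted mean, and nothing else in the visible plan corrects for it. Averaged over studies stopped for that reason, the mean overstates benefit. The direction follows from the stopping provision; the size does not follow from the documents. In the assumed cases it is about 0.03 SD or less when truth is better than expected and a stop is very likely, 0.10 to 0.34 SD when truth equals expected, and 0.4 to 0.5 SD for stops that occur in 2% of studies or fewer. Over all studies the average is about 0.05 SD or less.

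It would go too far to call the study's estimate biased in general, or to treat any of these figures as the bias of this study. The open choice of historical comparator exists whether or not the study stops early. It is a secondary point under 8.1 and is not evidence for this one. The amendment should be made, but the matter is not critical for a feasibility study.

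**What to change.** 1. In 6.8, delete the favourable-results stop. State that favourable interim results will not end enrolment, including as a valid scientific reason under 13.2. Safety and administrative stops stay as they are.
2. The unfavourable stop may stay. Fix its endpoint, minimum n and threshold by dated amendment, disclose any outcome reviews already done, and note that studies reaching 36 are then biased slightly toward benefit (about 0.02 to 0.18 SD in the assumed cases).
3. If the study stops early on outcome, report the reason, the planned and actual n, and the primary mean with in-progress subjects included. Add a confidence interval and a caveat on early-stopping bias.
4. Separately, in 8.1: choose the historical source by a rule dated before further outcome review, and give the comparison with an interval that includes the comparator's standard error.

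**Cost.** Amendment wording in 6.8 and 8.1, and a literature search. The sponsor loses the option to stop early for good results, within a cap of 36 that takes about 18 months to enrol. One gap remains: 13.2 still lets the sponsor end the study by discontinuing development, so poor results could act through that route. If outcome reviews have already begun, a threshold or comparator fixed now is not blind to them, so those reviews should be disclosed alongside both.

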6.9 Subject Compensation

Subjects will [REDACTED] compensation for taking part in all study visits. Compensation will be based on the subject completing milestones within the study. The disbursement schedule will be as follows:

- 0 after the completion of Visit 1 – Consenting
- [REDACTED] after the completion of Visit 2 – Lead Placement and Testing
- [REDACTED] after the completion of each Visit 4, 5 (only one instance), 7, 11, and 13
- [REDACTED] after the completion of each Visit 6, 8, 9, 10, and 12

If a subject volunteers to participate in an additional Visit 2 (returns for another session of stimulation testing or for a lead replacement), the subject will receive [REDACTED] compensation at the completion of that visit. All requirements for Visit 2 will be repeated.

In addition to payment for study participation, transportation can be arranged for subjects or mileage compensation can be provided at the current federal mileage rate for travel to visits.
[REDACTED]

7.0 DATA MANAGEMENT

7.1 Subject Screening and Identification Log

A subject screening log will be completed at the investigational site for all subjects who were considered for the study. Those individuals who are excluded will be listed along with the reason for exclusion. Any subject who signs an Informed Consent and does not proceed with procedures associated with lead placement or fails to meet eligibility (e.g., positive pregnancy test) will be considered a screen failure. The Informed Consent form will be filed in the screening binder. The Subject identification log will be completed for subjects enrolled in the study.

7.2 Data Collection

Case Report Forms (CRFs) will be completed for each subject who signs an informed consent form up until the point of discharge from the study. CRFs will be completed and maintained in a fashion that is consistent with accepted Good Clinical Practices. CRFs will be completed in permanent blue or black ink and all entries will be made in a legible fashion. All fields will be completed. If necessary, corrections will be made by using a single line strikeout with the initials and date of the person making the correction. The corrections will be made so as not to obscure the original data. Correction fluid or correction tape may not be used. Where specified, the Principal Investigator must sign and date the CRFs and questionnaires.

All CRFs will be stored in a locked storage facility (either a locked office or a locked cabinet).

7.3 Subject Numbering

Eligible (*i.e.*, meeting all selection criteria through Visit 2) consecutive subjects will be given a unique alpha - numerical Subject ID number. Two-digit numbers will be assigned consecutively to each subject starting at 01. The letter will designate the site. A master list linking the subjects to the unique Subject ID numbers will be kept by the study staff in a secure location.

7.4 Confidentiality of Data

Every effort will be made to protect subject confidentiality. Subject names and personal identifiers will not appear in any publications resulting from this work. Subjects will be informed that the sponsor, the IRB, and regulatory authorities will have access to records that identify them as individuals. All applicable HIPAA regulations will be followed.

7.5 Data Processing

SPR Therapeutics, LLC will be responsible for database creation, data entry, generation of database queries, and data analysis.

All CRFs will be monitored by SPR Therapeutics personnel (or their authorized representatives). Completed, monitored forms will be returned to SPR Therapeutics for entry into the database. Visual checks will be completed for generation of site queries. The Investigational Site will be queried for missing data, inconsistent data, or illegible information via Query Forms. Following site query resolution, all Query Forms will be returned to SPR Therapeutics for inclusion into and/or modification of the study database.

8.0 DATA ANALYSIS

All primary and secondary outcome data will be analyzed and reported. Each site or individual surgeon may be analyzed separately. This study is a case series involving up to 36 subjects. The purpose of this study is to determine the treatment effect of PNS therapy for the treatment of knee pain following TKA. The outcomes of this study will also provide preliminary data to support and refine subsequent studies of this therapy for postoperative knee pain following TKA.

8.1 Analysis of Outcomes and Exploratory Measures

A table of outcomes and exploratory measures to be collected during the study can be found in Appendix A.

Question 5 of the Brief Pain Inventory-Short Form (BPI-5) is an 11-point numerical rating scale rating “Average Pain”. The BPI-5 will be measured at Visit 1 to establish a baseline score, as well as daily during stimulation and monthly post-EOT. For each subject, the mean over the first 4 weeks following TKA surgery will be calculated. An overall mean across all subjects for the first 4 weeks following TKA surgery will be calculated as well. This outcome will also be compared to historical controls (e.g., published data).

Additionally, sub-analyses will be performed to determine the mean over different post-operative phases (such as acute (e.g., days 1-7) or subacute (e.g., days 7-28)); calculate the mean for each subject and across subjects up to End of Treatment (week 6); and evaluate the proportion of subjects with pain below a certain threshold (e.g., 4/10).

Subjects will also rank their daily “Average Pain” (BPI-5) while walking. These data will undergo the same analysis as listed above for the standard BPI-5. This outcome will also be compared to historical controls (e.g., published data).

At the weekly visits during stimulation, subjects will be asked to report their weekly “Average Pain” (BPI-5) while at rest. The mean over different intervals (such as weeks 1-4 or weeks 1-6) will be calculated.

At each study visit, pain treatments and analgesic usage will be recorded. Changes in analgesic usage will be calculated using morphine equivalent dosing (MED). The usage of analgesics over various intervals (such as weekly averages, during weeks 1-4, etc.) will be calculated.

Medication usage will also be compared to pain scores to examine the correlation between analgesic usage and pain. The time to cessation of opioid will be determined. Also at each study visit, subjects will be queried for opioid related side effects. The number of effects noted over various intervals will be calculated.

Range of motion [REDACTED] will be collected at visits before, during, and after treatment. The time to achieve milestones (e.g., 90 degrees flexion, 100 degrees flexion) will be calculated for each subject and across all subjects. The mean flexion, extension, and range of motion (flexion – extension) across all subjects will be determined. The same will be calculated for passive ROM and active ROM.

Functional tests performed during the study will include the Timed Up and Go (TUG) test, the Six-Minute Walk Test, and the Fixed Distance Walk Test. The TUG test will be analyzed to determine the mean time across subjects at each time point. The 6MWT will be used to calculate the mean distance across subjects at each time point. Data from the Fixed Distance Walk Test will be used to compute the mean time across subjects at each time point.

Surveys performed during the study will include the Western Ontario and McMaster Universities Arthritis Index (WOMAC), Pain Interference (as measured by question #9 of the Brief Pain Inventory), Patient Global Impression of Change (PGIC), time to meet recovery milestones, Subject Satisfaction Survey, and Clinician Satisfaction Survey. The WOMAC will be used to calculate a mean total score across all subjects, means score of specific subsections or individual questions, and to calculate differences in scores post-operatively compared to pre-operatively. BPI-9 will be used to calculate differences in scores post-operatively compared to pre-operatively for individual subjects as well as across all subjects. A mean PGIC score will be calculated across all subjects. The time to meet recovery milestones will be used to compute the mean number of days to achieve each milestone. Frequency of answers will be determined for specific questions of the Subject Satisfaction Survey and Clinician Satisfaction Survey.

Throughout the study, subjects will complete self-shaded diagrams of areas of pain

The mean and standard deviation of the percent overlap will be calculated across subjects.

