Pain may be assessed before, during, and/or after ROM measurements (e.g., at maximum flexion, at maximum extension) using Question 6 of the Brief Pain Inventory-Short Form (BPI-6). BPI-6 rates “Pain right now” on an 11 point numerical rating scale, with one end representing “No pain” (0) and the other end representing “Pain as bad as you can imagine” (10).

Timed Up and Go (TUG) Test

The TUG test is an objective measure of mobility. The subject begins by sitting in a standard chair (e.g., uncushioned chair with armrests and seat height of 46 cm). A line is placed on the floor approximately ten feet (i.e., 3 meters) away. The subject is timed while they stand up, walk to the line at a normal, safe pace, walk back to the chair, and sit down. The test is reliable, a good indicator of the patient’s recovery from TKA, and easy to complete. The TUG test will be completed at various time points, including: the baseline visit (Visit 1), once during the in-hospital treatment visits, such as the anticipated last visit before discharge (when deemed safe by clinical staff), and during visits following hospital discharge. Regular footwear should be worn, and the use of any assistive devices (e.g., canes, walkers) is permitted and will be recorded.

Six minute walk test (6MWT)

The 6MWT records the total distance the subject can walk in 6 minutes. It is frequently used to measure endurance and is validated as a measure of mobility following TKA. Assistive devices (e.g., canes, walkers) may be used during the 6MWT. If the 6MWT can be conducted, then the total distance walked is recorded (subjects unable to walk at all will receive a score of 0 meters). Subjects will be allowed to rest during the test if necessary. The 6MWT may be administered at Visit 1 (before TKA surgery) and at visits following hospital discharge.

Fixed distance walking test

Subjects may be asked to walk a fixed distance (e.g., 20 meters) with or without an assistive device or help from clinical staff, and the time required to walk this distance may be measured to assess walking speed. Also, the first day following TKA surgery at which the subject can walk specific distances (e.g., 20 meters) may be recorded. The test may be administered at Visit 1 and once during the in-hospital treatment visits, such as the anticipated last visit before discharge (when deemed safe by clinical staff).

Western Ontario and McMaster Universities Osteoarthritis Index (WOMAC)

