6.5.5 In-Hospital Treatment: (Visits 5a, b, c, etc.)

On each day of in-hospital treatment (starting at POD 1), clinical/study staff will visit the subject in the subject’s unit. If necessary, pads and/or batteries will be replaced and stimulation parameters may be adjusted. [REDACTED]

Maintenance and care of the leads and lead exit sites will be performed, including visual inspection and bandage changes, if necessary. The following outcome measures may be assessed during each Visit 5:

Pain [REDACTED]

Completion of daily diary [REDACTED]

- Range of motion ([REDACTED] and pain during ROM)
- Fixed Distance Walk Test (only at the anticipated last visit before discharge)
- TUG Test (only at the anticipated last visit before discharge)
- WOMAC (only at the anticipated last visit before discharge)

BPI-9 [REDACTED]

- Patient Global Impression of Change (PGIC) (only at the anticipated last visit before discharge)
- Time to recovery milestones
- Current pain treatments/analgesic usage
- Assess for opioid-related side effects

In addition, subjects will be queried for adverse events. Outcomes requiring physical function of the subject (such as Fixed Distance Walk Test or TUG Test) must be assessed by the physical therapy staff for the in-hospital visits. All functional outcomes will only be administered if deemed safe by the staff. If it is deemed unsafe to complete a test or if the subject is unable to complete a test, it will not be considered a protocol deviation.

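### TUG and Fixed Distance Walk means cover only subjects able to do the test, and the 6MWT can record inability as 0 m or as missing

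*Combined protocol and SAP*

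**What the plan says.** Section 8.1 gives one sentence of analysis to each functional test. For the TUG: "The TUG test will be analyzed to determine the mean time across subjects at each time point". For the Fixed Distance Walk: "Data from the Fixed Distance Walk Test will be used to compute the mean time across subjects at each time point". For the 6MWT: "The 6MWT will be used to calculate the mean distance across subjects at each time point".

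Other sections determine who contributes a value:

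- Section 6.5.5 (in-hospital visits, where the TUG and Fixed Distance Walk are done): "All functional outcomes will only be administered if deemed safe by the staff". It adds that, if a test is unsafe or "if the subject is unable to complete a test, it will not be considered a protocol deviation". No substitute value is given.
- The functional-outcomes footnote to Appendix A applies the same safety condition to all three tests and does not confine it to the hospital stay. It is the only place where the condition reaches the 6MWT.
- Section 3.3, on the 6MWT: "If the 6MWT can be conducted, then the total distance walked is recorded", with the parenthesis that "subjects unable to walk at all will receive a score of 0 meters".
- Section 8.2 provides recall and imputation rules for pain diaries only.

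The schedules differ. The TUG is done at baseline, once in hospital and at in-person visits after discharge. The Fixed Distance Walk is done at Visit 1 and once in hospital. The 6MWT is done at Visit 1 and after discharge.

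**The concern.** A timed test has no value for a subject who cannot do it. Since the plan supplies none, a mean across subjects can only be a mean across those who completed the test. When the reason is poor function, the missing results are the worst ones, and the group being averaged changes as subjects recover.

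This has a different effect on each test. The TUG is repeated after discharge, so slow subjects can join the average later and pull it the wrong way. The Fixed Distance Walk has no later assessment; its in-hospital mean simply understates the loss of function since Visit 1. The 6MWT does have a score for inability, but a test withheld as unsafe gets no score, so similar subjects may be handled differently, including between sites (up to 6 are planned).

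Section 3.3 says the secondary outcomes are to help design future studies. Means and standard deviations from a selected and shifting subset are a poor basis for choosing an endpoint or a sample size.

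**Working it through.** The plan gives no figure on this point, so there is nothing to reproduce. The maximum of 36 subjects is from Section 5.2. All times, distances and numbers unable below are assumptions. All 36 are taken as due at each visit, and all as able at the later one.

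**TUG: can the mean worsen while everyone improves?**
Let u be the number unable at the first test. The able average 20 s at first and 18 s later (10% faster), and the newly able average T.

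- First mean = 20 s, over 36 − u subjects.
- Later mean = [(36 − u) × 18 + u × T] / 36.
- The mean worsens when T exceeds [36 × 20 − (36 − u) × 18] / u.

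For u = 6: (720 − 540) / 6 = 30 s. With T = 45 s, the later mean is (540 + 270) / 36 = 22.5 s against 20.0 s, 12.5% worse, although all 36 improved.

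The threshold for T depends on u and on how much the able improve:

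| Unable at first | Able 10% faster (18 s) | Able 20% faster (16 s) |
|---|---|---|
| 4 | 36.0 s | 52.0 s |
| 7 | 28.3 s | 36.6 s |
| 11 | 24.5 s | 29.1 s |

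With 10% improvement and fewer unable, the threshold is 42 s for 3 subjects, (720 − 594) / 3, and 54 s for 2, (720 − 612) / 2.

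**Do the proposed summaries behave better?** Use the u = 6 case and, for simplicity, give all 30 able subjects the same time. The median with the 6 ranked worst goes from 20 s to 18 s. The change in the same 30 subjects is −2 s. Both move in the right direction.

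**Fixed Distance Walk.** No number is needed. A subject unable because of the operated knee has done worse than any subject who finished, so leaving that subject out can only make the in-hospital result look better. With no later test, nobody can re-enter.

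**6MWT: effect of coding alone.** Assume the able average 300 m. If k non-walkers are unscored, the mean is 300 m. If they are scored 0 m, it is (36 − k) × 300 / 36:

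- k = 2: 283 m
- k = 3: 275 m
- k = 4: 267 m
- k = 7: 242 m

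The composition effect also exists here, but not always. With 7 unscored at first, the able improving 10% to 330 m and the newly able walking 100 m, the mean falls from 300 m to (29 × 330 + 7 × 100) / 36 = 285 m. With 2 unscored, the able improving 5% to 315 m and the newly able walking 50 m, it is (34 × 315 + 2 × 50) / 36 = 300.3 m, so there is no reversal.

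**The case against.** The strongest reply is that few subjects may be untestable. The in-hospital TUG is planned for the last expected visit before discharge. Discharge criteria may include walking 30 m and some stairs (Section 3.3), whereas the TUG needs about 3 m each way with walking aids allowed. This stands as a limit on size: the 6 of 36 is not from the documents, and with 2 or 3 unable a reversal needs very slow newcomers. It does not remove the problem. Discharge criteria differ between hospitals, and some subjects go to inpatient rehabilitation or skilled nursing facilities.

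Inability is also partly visible elsewhere. Walking milestones and the first day a set distance is walked may be recorded, and WOMAC physical function is analysed as a change from before surgery. These are real but partial, some are optional, and none is tied to the functional means.

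For the 6MWT, a test judged unsafe need not mean a subject who cannot walk; the reason may have nothing to do with the knee. That is correct. The inconsistency concerns only subjects unable to walk because of the operated knee.

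A reader might infer more than the documents support:

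- **That both timed tests can reverse over time.** The Fixed Distance Walk has no assessment after the in-hospital one.
- **That a comparison of function with external benchmarks is compromised.** Historical controls are specified for pain only.
- **That the case report form lacks a reason for a missed test.** The forms are not in the documents, so this cannot be checked.

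**Conclusion.** The point holds as a defect in how the functional secondary outcomes are summarised. Followed as written, Section 8.1 gives post-operative TUG and Fixed Distance Walk means over able subjects only, without saying how many those are. That the mean is restricted in this way is an inference, but with no value defined for inability there is no other workable reading.

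For the TUG, a mean that worsens while everyone improves is possible, not certain. It depends on how many are unable at first and how slow they are later; with 10% improvement from 20 s, the threshold runs from 54 s (2 unable) to 24.5 s (11 unable). For the Fixed Distance Walk, the bias is a favourable in-hospital mean. For the 6MWT, coding alone could shift the mean by 25 m if 3 of 36 cannot walk and the rest average 300 m.

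It would be too strong to say that no functional result can be trusted. The means cannot be interpreted without the numbers behind them. The outcomes are descriptive, in a single-arm feasibility series, and the primary pain endpoint is untouched. The plan should be changed, but the study does not depend on it.

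**What to change.** In Section 8.1:

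1. Beside each functional summary, at each time point, report the number of subjects due, able, unable and judged unsafe, with the reason. Record the reason on the case report form if it is not already there.
2. Summarise the timed tests so that subjects unable, or judged unsafe because of the operated knee, stay in. A median with them ranked worst is one choice; walking speed with 0 for inability is another and suits the Fixed Distance Walk. Keep the mean among those able alongside, labelled as such.
3. Show change from baseline in the same subjects.
4. For the 6MWT, apply the 0 m score equally to subjects unable to walk and to those judged unsafe because of the operated knee. Treat tests missed for other reasons as missing. Align the wording in Section 3.3 and the Appendix A footnote.

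The staff's judgement on whether a test is safe stays as it is. The cost is some analysis wording and at most one extra form field, with no additional tests. The drawback is that early functional summaries may look less favourable.
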